##### Metabolic markers:

- BMI, waist circumference, waist:hip ratio, HBA1C and HOMA-IR
- Serum lipid profile – total cholesterol, triglycerides, LDL and HDL fractions

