## 14. Concurrent medications including:

- Anti-NASH therapy(s) taken for more than 10 continuous days in the last 3 months. These include S-adenosyl methionine (SAM-e), betaine, milk thistle, bacterial probiotic supplements (other than yoghurt or other natural food sources), vitamin E and gemfibrozil.
  - NOTE: If determinant biopsy is performed while on stable treatment – subject is eligible;
  - Wash out for any of the anti-NASH therapies is as follow: under 10 days no washout required, more than 10 days and up to 3 months treatment requires 6 weeks washout. Any treatment of over 3 months would require to re-biopsy to ensure histological eligibility
  - Thiazolidinediones (glitazones), dipeptidyl peptidase 4 inhibitors (gliptins) or glucagon-like peptide-1 analogs in the last 6 months.  
NOTE: if determinant biopsy is performed while on stable treatment of at least 6 months – subject is eligible.
  - NOTE: Allowable anti-diabetic treatment includes metformin and/or sulfonylureas administered at constant dose for at least 2 months prior to study entry
  - NOTE: Subjects treated with Insulin are eligible if clinically stable on insulin treatment (i.e. no recurrent acute hypo-/hyperglycemic episodes diagnosed clinically and by Glucose serum levels of <50 mg/dL and >200 mg/dL respectively) for at least 2 months prior to study entry
- immune modulatory agents including:
  - Within 3 months of study entry:
    - systemic steroids for more than 7 days
    - daily treatment with multiple non-steroidal anti-inflammatory drugs (such as aspirin >100mg/day, ibuprofen, naproxen, meloxicam, celecoxib) for more than 1 month
  - In the last 12 months:
    - azathioprine, 6-mercaptopurine, methotrexate, cyclosporin, anti-TNF $\alpha$  therapies (infliximab, adalimumab, etanercept) or anti-integrin therapies (namixilab)
- more than 10 consecutive days oral or parenteral antibiotics within 4 weeks prior to study entry NOTE: subjects administered with antibiotics for more the 5 days prior to study entry would not be included in the stool and PBMC analysis)
- Variable dose of anti-lipidemic agents (HMG Co-A reductase inhibitors – “statins”) in the 3 months prior to Screening

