### 7.3.6 Safety Laboratory Assessments

Blood will be collected at Screening, Baseline, and scheduled clinic visits (except D3) and at the Withdrawal visit if applicable. These should be collected within the visit window period required for the visit date (see [Section 7.4](#)). Urine will be collected at Screening only.

Clinical chemistry will be performed at the Baseline visit and scheduled clinic visits (except D3) with the subject having fasted for at least 8 hours before sample collection. HOMA-IR score will be calculated when fasting glucose and insulin measurements have been reported, according to the HOMA-IR algorithm (Appendix C).

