**Table 3: Safety Laboratory Parameters**

Test	Parameters
Hematology (Screening, Baseline, D7, D14, W4 and 4 weekly thereafter)	Hemoglobin, hematocrit, red blood cell (RBC) and RBC morphology, white blood cell (WBC) and differential WBC count, platelet count, mean corpuscular volume (MCV), mean corpuscular hemoglobin concentration (MCHC) and neutrophil count.
Coagulation (Screening, Baseline, D7, D14, W4 and 4 weekly thereafter)	Prothrombin time (PT), partial thromboplastin time (PTT), and International Normalized Ratio (INR).
Clinical Chemistry (Screening, then fasting at Baseline, D7, D14, W4 and 4 weekly thereafter)	Sodium, potassium, chloride, bicarbonate, blood urea nitrogen, creatine phosphokinase, creatinine, total protein, albumin, serum amylase (fractionated if > upper limit of normal (ULN)), lipase, phosphate, GGT, AST, ALT, alkaline phosphatase, total bilirubin, calcium, uric acid, glucose and insulin. CRP and C-peptide will be included at Baseline, W4, W12 and W24 only.
Serum lipid panel (Baseline, D7, D14, W4 and 4 weekly thereafter)	Total cholesterol, triglycerides, high and low density lipoproteins
Blood glucose (average) (Screening, W12 and W24)	HBA1c
Urine (Screening only)	Specific gravity, protein, glucose, blood, leukocytes, pH, ketones, bilirubin, urobilinogen, nitrites

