#### 9.2.2 During the Study Dosing Period

Throughout the study medication dosing period, subjects may not receive any of the following concomitant medications:

- other anti-NASH therapy(s) including, SAM-e, betaine, milk thistle and probiotic supplements (not including yoghurt);
- thiazolidinediones (glitazones), dipeptidyl peptidase 4 inhibitors (gliptins) or GLP-1 analogs, unless the subject was recruited on a stable dose.
- Allowable anti-diabetic treatment includes insulin, metformin and/or sulfonylureas administered at constant dose for at least 2 months prior to study entry;
- immune modulatory agents including
  - systemic steroids for more than 7 days
  - multiple non-steroidal anti-inflammatory drugs such as aspirin (>100mg/day), ibuprofen, naproxen, meloxicam, celecoxib;
  - azathioprine, 6-mercaptopurine, methotrexate, cyclosporin, anti-TNF $\alpha$  therapies (infliximab, adalimumab, etanercept) or anti-integrin therapies (namixilab).

Treatment with antilipidemic agents (HMG Co-A reductase inhibitors – “statins”), vitamin E, gemfibrozil and allowable antidiabetic treatment (metformin and/or sulfonylurea) must be stable throughout the study.

Antibiotics should be taken if clinically indicated but avoided where possible.

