**APPENDIX C HOMEOSTATIC MODEL ASSESSMENT OF INSULIN RESISTANCE SCORE**

The following formula is to be used to calculate the HOMA-IR score based on laboratory reported measurements of serum fasting glucose and insulin as required:

$$\text{HOMA-IR} = \frac{\text{glucose (mmol/L*)} \times \text{insulin (mU/mL)}}{22.5}$$

\* To convert mg/dL to mmol/L, divide by 18

**APPENDIX D ALCOHOL USE DISORDERS IDENTIFICATION TEST (AUDIT)  
QUESTIONNAIRE**

Please circle the answer that is correct for you:

1. How often do you have a drink containing alcohol?

- Never
- Monthly or less
- 2-4 times a month
- 2-3 times a week
- 4 or more times a week

2. How many standard drinks containing alcohol do you have on a typical day when drinking?

- 1 or 2
- 3 or 4
- 5 or 6
- 7 to 9
- 10 or more

3. How often do you have six or more drinks on one occasion?

- Never
- Less than monthly
- Monthly
- Weekly
- Daily or almost daily

4. During the past year, how often have you found that you were not able to stop drinking once you had started?

- Never
- Less than monthly
- Monthly
- Weekly
- Daily or almost daily

5. During the past year, how often have you failed to do what was normally expected of you because of drinking?

- Never
- Less than monthly
- Monthly
- Weekly
- Daily or almost daily

6. During the past year, how often have you needed a drink in the morning to get yourself going after a heavy drinking session?

- Never
- Less than monthly
- Monthly
- Weekly
- Daily or almost daily

7. During the past year, how often have you had a feeling of guilt or remorse after drinking?

- Never
- Less than monthly
- Monthly
- Weekly
- Daily or almost daily

8. During the past year, have you been unable to remember what happened the night before because you had been drinking?

- Never
- Less than monthly
- Monthly
- Weekly
- Daily or almost daily

9. Have you or someone else been injured as a result of your drinking?

- No
- Yes, but not in the past year
- Yes, during the past year

10. Has a relative or friend, doctor or other health worker been concerned about your drinking or suggested you cut down?

- No
- Yes, but not in the past year
- Yes, during the past year

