7.3 Secondary efficacy analyses

The following analyses of secondary efficacy will be performed on the FAS population. However, if the results for the primary efficacy analysis differ across populations, the ITT and PP populations may also be subject to secondary efficacy analysis. For the analyses detailed in this section and section 7.4, inferential statistical analysis will be performed on the same basis as for the primary endpoint. For those values that are recorded at 3 or more time-points, the baseline value will be included in the repeated measures analysis as a covariate. For analyses with only a baseline and final value, t-tests or Wilcoxon rank-sum tests will be performed depending on the distribution of the data. In addition to this, the mean change from baseline for all relevant variables will be assessed and presented.

Serum concentrations of IMM-214E bovine antibodies (including but not limited to: maximum and minimum observed concentration, area under the concentration-time curve, and (if feasible) elimination half-life) will be summarised and tabulated by visit and time point. Pharmacokinetic coefficients, including but not limited to, maximal and minimal concentration, area under the concentration curve and, if possible, elimination half-life will also be summarised and tabulated with change from Baseline by visit.

Body mass index (BMI), waist circumference and waist:hip ratio with change from Baseline will be summarised and tabulated by visit and treatment group.

HbA1c, glucose and homeostatic model assessment of insulin resistance (HOMA-IR) will be summarised and tabulated with change from Baseline by visit and treatment group.

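### HOMA-IR is analysed in all dosed patients, including insulin users, in whom the score partly reflects injected insulin; the SAP should define the main HOMA-IR analysis by insulin use at Baseline

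*Protocol*

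**What the plan says.** **Who may enter.** Exclusion criterion 14 (Protocol 6.3) carries a note: "Subjects treated with Insulin are eligible if clinically stable on insulin treatment". It defines stability by the absence of recurrent low- or high-glucose episodes over at least two months, not by a fixed dose.

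**What may be used on study.** Protocol 9.2.2 reads: "Allowable anti-diabetic treatment includes insulin, metformin and/or sulfonylureas administered at constant dose for at least 2 months prior to study entry". A later sentence in the same section reads: "allowable antidiabetic treatment (metformin and/or sulfonylurea) must be stable throughout the study". That sentence does not name insulin.

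**How the score is formed.** Protocol 4.2 lists the metabolic secondary endpoints as "BMI, waist circumference, waist:hip ratio, HBA1C and HOMA-IR". Appendix C gives glucose times insulin divided by 22.5, "based on laboratory reported measurements of serum fasting glucose and insulin as required". Section 7.3.6 adds: "HOMA-IR score will be calculated when fasting glucose and insulin measurements have been reported". Neither place makes an exception for insulin users. Table 1 schedules HOMA-IR at Baseline, Days 7 and 14, and every four weeks from Week 4 to Week 24.

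**How it is analysed.** SAP 7.3 says "homeostatic model assessment of insulin resistance (HOMA-IR) will be summarised and tabulated with change from Baseline", by visit and treatment group. The population is the FAS (all dosed subjects), and inference follows the primary endpoint's approach, with the baseline value as a covariate where there are three or more time points. SAP section 12 also lists ITT and PP tables. The subgroup factors in SAP 7.2 are hepatic fat, HbA1c, ALT, fibrosis, inflammation and ballooning. Insulin use is neither a subgroup factor nor a randomisation stratum (Protocol 8.1).

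**What else is measured.** Protocol Table 3: "CRP and C-peptide will be included at Baseline, W4, W12 and W24 only". The SAP does not name C-peptide.

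**The concern.** HOMA-IR reads fasting insulin as the patient's own response to the fasting glucose level. If part of the measured insulin was injected, the product also depends on the dose and on when it was given. The eight-hour fast controls food, not injection timing.

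Two things are at stake. First, within-patient variation in injected insulin enters the change from Baseline as noise. Second, if treatment alters the need for insulin, dosing changes may differ between arms, and randomisation does not remove that. The direction can even be wrong: more injected insulin with better glucose control can read as worse resistance. Effect on glucose metabolism is a stated secondary objective, and HOMA-IR is its insulin-resistance measure.

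**Working it through.** The documents give no power, SD or expected effect for HOMA-IR, so there is no plan figure to reproduce. Apart from the Appendix C formula and 40 patients per arm, every input below is an assumption.

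**1. Behaviour of the formula in one patient.** HOMA-IR = glucose × insulin / 22.5. Assume the patient's own insulin stays at 15 units and the assay detects injected insulin.

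- No injected insulin, glucose 8 mmol/L: 8 × 15 / 22.5 = 5.33.
- 10 units of injected insulin detected: 8 × 25 / 22.5 = 8.89, an artefact of about 3.6.
- Detected injected insulin then rises to 20 units and glucose falls to 7 mmol/L: 7 × 35 / 22.5 = 10.89.

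The last step is 10.89 / 8.89 − 1 = +22.5%, although glucose improved.

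**2. Chance imbalance between arms.** With a share f of users, the SD of the between-arm difference in that share is √(2f(1−f)/40). For f = 5% this is 4.9 percentage points, and for f = 30% it is 10.2. Randomisation balances users on average, but not closely at this sample size.

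**3. Power with and without users.** Take a two-sided 5% t-test on log change, with SD 0.5 in non-users and a true 30% reduction in non-users, so the effect is −ln(0.7) = 0.357. Let q be the share of users and s their extra SD.

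- Users excluded: 40(1−q) per arm, effect 0.357, SD 0.5.
- Users included, no response in users: 40 per arm, effect 0.357(1−q), SD √(0.25 + q·s²).
- Users included, full response: 40 per arm, effect 0.357, same SD.

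For q = 10%:

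- Excluded: 36 per arm, 0.357 / (0.5 × √(2/36)) = 3.03, power 85%.
- Included, no response, s = 1.0: effect 0.321, SD √0.35 = 0.592, 0.321 / (0.592 × √(2/40)) = 2.43, power 67%.
- Included, full response, s = 0.5: SD √0.275 = 0.524, 0.357 / (0.524 × √(2/40)) = 3.04, power 85%.

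| Share of users | Excluded | Included: no response, s = 1.0 | Included: no response, s = 0.5 | Included: full response, s = 1.0 | Included: full response, s = 0.5 |
|---|---|---|---|---|---|
| 5% | 87% | 78% | 83% | 82% | 87% |
| 10% | 85% | 67% | 77% | 76% | 85% |
| 20% | 80% | 47% | 63% | 65% | 82% |
| 25% | 78% | 39% | 56% | 61% | 80% |

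Against exclusion, the worst column loses 9, 18, 33 and 39 points. The best column loses nothing and gains up to about 3 points (80.5% against 77.5% at a 25% share, before rounding).

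**4. The SAP's fallback test.** The SAP does not plan a plain t-test. If the data are not normal it moves to ranks and then to permutation (SAP 7.2). Simulating the worst column with a rank-sum test gives roughly 80, 75, 60 and 52%. The loss is smaller, but it remains.

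**The case against.** The strongest reply is that the harm is assumed, not shown. The documents give no share of insulin users, no assay description and no HOMA-IR SD. If users respond like everyone else with modest extra variability, keeping them costs nothing. That stands, and it rules out quoting any single power loss as the trial's.

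The plan also has partial protections:

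- Section 9.2.2 asks for a constant dose before entry.
- Samples are fasting.
- Randomisation is stratified by HbA1c, and HOMA-IR tables by HbA1c subgroup are planned.
- Medians and quartiles are reported, and the rank and permutation fallback limits the pull of extreme values on the tests.

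These reduce noise and imbalance. They do not restore the score's meaning in a patient on insulin, and HbA1c groups do not separate insulin users from diabetic patients on oral agents.

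A reader might infer that HOMA-IR results will be inflated by a large percentage. If users' measured insulin were tripled, the arm mean would rise by 2q, or 10% to 50% for shares of 5% to 25%. That is a rise in level within every arm. The endpoint is change from Baseline compared between randomised arms, where a persistent artefact partly cancels and is balanced on average. The documents do not support reading the level shift as bias in the treatment comparison.

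Finally, HOMA-IR is one of several secondary markers in a trial that Protocol section 12 calls exploratory, and no power is claimed for it. That limits the weight of the point but does not remove it.

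**Conclusion.** The point holds for the insulin-treated subset. The plan admits these patients, computes HOMA-IR from their measured insulin and analyses them with everyone else, so this secondary endpoint is partly invalid as an insulin-resistance measure in that subset. The consequences are added noise and, if on-study insulin changes differ by arm, possible bias in the change from Baseline.

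The size cannot be determined from the documents. On the assumptions shown, including users changes power by anything from a loss of about 9 to 39 points (no response in users, extra SD 1.0) to a gain of up to about 3 points (full response, extra SD 0.5). The case for change rests on interpretability rather than on a particular power figure.

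A reader might also infer that the trial's main result is compromised. It is not: the MRI primary endpoint and its power calculation do not use HOMA-IR. Beyond this secondary endpoint, only the staging by HOMA-IR in Protocol 7.3.13 shares the problem. This should be corrected before unblinding, as a cheap repair to a secondary endpoint.

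**What to change.** In SAP 7.3, and for the matching ITT and PP tables:

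- Make the main HOMA-IR analysis the patients not on insulin at Baseline. This is a pre-randomisation definition, so the randomised comparison is kept within the subset. Do not restrict visit by visit to times without insulin: that selects on post-randomisation insulin use, which treatment may affect.
- State one analysis rule for insulin started on study. Using values as measured keeps the data but lets the artefact back in. Setting later values to missing removes the artefact but relies on the missing-data assumptions. Choose one before unblinding.
- Keep the all-FAS analysis as supportive.
- Summarise fasting C-peptide by arm for all patients at Baseline and Weeks 4, 12 and 24. It reflects the patient's own insulin secretion. It supports the HOMA-IR result but does not replace it.

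The sponsor must also reconcile criterion 14 (clinical stability) with section 9.2.2 (constant dose before entry, and an on-study stability sentence that does not name insulin). No clinical rule is proposed here.

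The cost is SAP wording and somewhat fewer patients in the main HOMA-IR analysis: 30 rather than 40 per arm if 25% use insulin. No new visit, sample or eligibility change is needed, since Protocol section 9 already records concurrent medications and dose changes.

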## 15. The following laboratory abnormalities:

- Neutrophil count  $\leq 1.0 \times 10^9/L$
- Platelets  $<100 \times 10^9/L$
- Hemoglobin  $<10g/dL$
- Albumin  $< 3.5g/dL$
- International Normalized Ratio (INR)  $>1.5$
- Total bilirubin  $>1.5$  x upper limit of reference range (unless Gilbert’s syndrome or extrahepatic source as denoted by increased indirect bilirubin fraction)
- Either creatinine clearance  $\leq 60$  mL/minute calculated by Cockcroft-Gault or creatinine  $>1.5$ x upper limit of reference range (see Section 6.4.2).

## 16. Known substance abuse, including inhaled or injected drugs in the year prior to Screening

## 17. Cow milk allergy, lactose intolerance or any known or suspected hypersensitivity to study products

## 6.4 Other Study Eligibility Criteria Considerations

In order to assess any potential impact on subject eligibility with regard to safety, the investigator must refer to the relevant document(s) for detailed information regarding warnings, precautions, contraindications, adverse events, and other significant data pertaining to the investigational product(s) being used in this study. Such documents may include, but are not limited to, the Investigator's Brochure.

### 6.4.1 Contraception

All women of child bearing potential (defined as sexually mature women who have had menses within the preceding 24 months and have not undergone hysterectomy, bilateral oophorectomy or tubal ligation) must have a negative pregnancy test (with a sensitivity of at least 50IU/mL) performed at Screening and at Baseline.

Women of child bearing potential must agree not to attempt to become pregnant or undergo *in vitro* fertilization and, if participating in sexual activity that could lead to pregnancy, must use two reliable methods of contraception simultaneously while receiving protocol-specified medication and for 28 days after stopping the medication. Male subjects must agree to use two reliable methods of contraception simultaneously while receiving protocol-specified medication and for 28 days after stopping the medication if their partner is of child bearing potential.

A combination of two of the following methods must be used:

- Condoms (male or female) with or without a spermicidal agent
- Diaphragm or cervical cap with spermicide
- Intra Uterine Device
- Hormonal-based contraception

Women who are not of reproductive potential (who have been postmenopausal for at least 24 consecutive months or have undergone hysterectomy, bilateral oophorectomy or tubal ligation) are not required to use contraception.

### 6.4.2 Renal Function

Renal function eligibility may be determined by either estimated creatinine clearance calculated by Cockcroft-Gault formula or serum creatinine.

The Cockcroft-Gault Formula is:

$$\text{Creatinine clearance (mL/min)} = \frac{(140 - \text{age}) \times (\text{Bodyweight in kg}) \times (0.85 \text{ if female})}{72 \times \text{Serum creatinine (mg/dL)}}$$

## 6.5 Subject Enrollment

Before subjects may be entered into the study, Immuron requires a copy of the site's written institutional review board (IRB) or human research/independent ethics committee (HREC/IEC) approval of the protocol, informed consent form, and all other subject information, as applicable. All subjects or legally acceptable representatives must personally sign and date the consent form before enrolment.

All subjects who provide written informed consent will be sequentially assigned a Subject Number. This number will be used to identify the subject throughout the clinical study and must be used on all study documentation related to that subject. Subjects who meet the inclusion/exclusion criteria will be randomly assigned to treatment using a permuted block randomization.

All screening tests and procedures should be performed within the 45 days prior to enrolment in the study at Baseline, unless otherwise indicated. Randomization and enrolment will be conducted as described in [Section 8](#).

## 7. SCHEDULE OF ASSESSMENTS AND PROCEDURES

### 7.1 Study Schedule of Evaluations

The schedule of assessments is presented in [Table 1](#).

### 7.2 Study Procedures and Assessment Periods

The study procedures to be conducted for each subject enrolled in the study are listed below. Additional information on the study procedures is provided in [Section 7.4](#). Any deviation from protocol procedures must be noted in the source notes and the Sponsor notified.

Additional visits and/or assessments may be conducted as clinically indicated. For these additional assessments, data may be collected on unscheduled Case Report Form (CRF) pages provided, together with all adverse events (AEs) and concurrent medication that must be recorded throughout the study period.

